## Document and Version Control

This section records all changes made to the protocol for a specific study. In the table below, record each and every relevant change by indicating what changes were made.

Revision	Date (DD/Mmm/YYYY)	Revision Author	Comments/Changes
1.0	31/Oct/2013	[name]	Initial draft.
2.0	03/Dec/2014	[name]	Table 3: Updated Neonate III Weight to “≥ 2000g” Section 6.4: Updated Inclusion Criteria 1 and 2 Section 7.11: Removed Date of Birth, added Age Section 7.1.3: Removed reference to evaluation to be performed by two observers and a supervisor as this is a requirement of ISO 81060-2:2013 (E) Chapter 5 and therefore is not applicable to this study Section 7.1.3: Removed numbering of 7.1.4 as formatting was incorrect Section 7.1.3: Blood Pressure Assessments- Corrected verbiage to match ISO 81060-2:2013 (E) for #2
3.0	26/May/2015	[name], [name]	Revised as per Appendices A (Amendment 1) and Appendix B (Amendment 2) to include detail of changes in version 2.0 and 3.0.
4.0	18/Jan/2016	[name]	Revised as per Appendix C (Amendment 3) to include detail of changes in version 3.0 to 4.0.
5.0	30/Jun/2016	[name]	Revised as per Appendix D (Amendment 4) to include detail of changes in version 4.0 to 5.0.
6.0	16/Feb/2017	[name]	Revised as per Appendix E (Amendment 5) to include detail of changes in version 5.0 to 6.0.
7.0	03/Mar/2017	[name]	Revised as per Appendix F (Amendment 6) to include detail of changes in version 6.0 to 7.0.

## ABBREVIATIONS

AAMI	Association for Advancement of Medical Instrumentation
BP	BP
DCS	Data collection system
ECG	Electrocardiogram
GEHC	GE Healthcare
GxP	Good Processing Tools (validated research tools, not for commercial use)
LCS	Life Care Solutions
IABP	Intra-arterial blood pressure
IBP	Invasive blood pressure
ISO	International Standards Organization
MAA	Maximum amplitude algorithm
MAP	Mean blood pressure
NIBP	Noninvasive blood pressure
PAD	Peripheral Artery Disease
PDM	Patient Data Module (for CARESCAPE B650)
PSM	Patient Side Module (for CARESCAPE B650)
P sys	Systolic pressure
P t	Target pressure

**Study Title:** Measurement of NonInvasive Blood Pressure with DINAMAP SuperSTAT and Datex-Ohmeda with Intra-arterial Blood Pressure in Neonates through Adults and Special Populations (MISSION Trial)

**Study Number:** 123.04-2013-GES-0008

**Protocol:** 7.0

## 1. STUDY SYNOPSIS

**Study Title:** Measurement of NonInvasive Blood Pressure with DINAMAP SuperSTAT and Datex-Ohmeda with Intra-arterial Blood Pressure in Neonates through Adults and Special Populations (MISSION Trial)  
**Study Number:** 123.04-2013-GES-0008

**Research Type:**

- Clinical (human)
- Pre-Clinical (animal)
- External Bench

**Brief Description of Study Purpose:** This study is required to demonstrate that the non-invasive blood pressure (NIBP) measurement algorithms on two commercially available multifunction hemodynamic acquisition modules, the Patient Data Module (PDM) equipped with the DINAMAP® SUPERSTAT algorithm (“PDM-SUPERSTAT”) and the Patient Side Module (PSM) equipped with Datex-Ohmeda GE algorithm (“PSM-Datex-Ohmeda”), provide accurate NIBP measurements in accordance with the guidelines provided by the most recent International Organization for Standardization (ISO) 81060-2:2013.

Notably, the new ISO 81060-2:2013 supersedes the previous 2009 version of this standard, and this study is being conducted in accordance with the most recent applicable standards.

This study will assess neonate, infant, children, pediatric, adolescent, and adult patients as well as adults with chronic atrial fibrillation in a population that requires non-emergent heart catheterization.

**Sponsor Name:** GE Healthcare  

**Device/Product Description:**

Non-invasive blood pressure (NIBP) measurement algorithms of two multifunction hemodynamic acquisition modules compatible with the CARESCAPE Monitor B650 patient monitor are under study in this trial, as follows:

- **PSM-Datex-Ohmeda:** Patient Side Module (PSM) with Datex-Ohmeda GE NIBP algorithm.
- **PDM-SuperSTAT:** Patient Data Module (PDM) with DINAMAP® SuperSTAT NIBP algorithm.

The control used in this study is gold standard aortic invasive blood pressure (IBP). Data may be collected on the DASH® 4000 patient monitor equipped with the non-commercial GEHC DC-EDIT and GEHC DC-COLLECTOR GxP software that can be compared with data either manually collected from the NIBP CARESCAPE Monitor B650 monitor, or data may be collected using the GxP-validated GEHC PDM Data Collection Module, which is capable of collecting electronic data typically displayed using patient monitors. The GxP-validated systems used in this study serve the sole function of enabling the device to directly output data such as blood pressure waveforms and parameters to the computerized data collection system (DCS) for storage and analysis purposes.

**Regulatory Status:**

Pre-Market

*The commercial DASH® 4000 patient monitor (control system) equipped with GxP validated non-commercial DC-COLLECTOR and DC-Edit software programs for data collection is considered investigational. The acquisition modules PDM-SuperSTAT and PSM-Datex-Ohmeda with the PSM-Datex-Ohmeda and PDM-SuperSTAT algorithms and used on the CARESCAPE Monitor B650 and accessories are commercially available, The PDM is considered investigational when GxP-validated PDM Data Collection Module is used, which functions in the same manner as the PDM but with additional ability to collect research data typically displayed on a patient monitor. Though pre- and post- market devices are utilized, all aspects of the study will be considered investigational.*

Post-Market

Research Manager Name: [name]
	
Address: [name] [name]
 
Telephone: [contact]
 
E-mail: [contact]

Medical Monitor Name: [name]
	
Address: [name] [name]
 
Telephone: [name]
 
E-mail: [contact]

## 2. PRELIMINARY INVESTIGATIONS AND JUSTIFICATION

### 2.1. Literature Review

#### Introduction

Accurate blood pressure measurement is essential to providing optimal care in hospitals and other clinical settings, and non-invasive blood pressure (NIBP) has overwhelmingly become the contemporary clinical standard for blood pressure measurement. Accurate blood pressure (BP) measurement is dependent on a trained observer using validated, calibrated, and properly maintained equipment, which has led to increasing emphasis on adherence of commercial NIBP devices to validated standards for accuracy and reliability. While previous studies have shown that arterial waveforms can be accurately and reproducibly reconstructed using oscillometric algorithms, such as the DINAMAP® SUPERSTAT and Datex-Ohmeda GE algorithms studied in this trial, the accuracy of these NIBP measurement algorithms has also been shown to have high variability in patients with variant age and cardiac disease status. Thus, there is a need to evaluate these algorithms against a validated clinical standard applicable to commercial sphygmomanometers.

#### ISO 81060-2:2013

Because the widely-accepted International Organization for Standardization (ISO) 81060-2:2009 standard has recently been updated to the ISO 81060-2:2013 version, it is necessary to reassess algorithms that have been previously tested under the predicate standard under the newest available standard in order to be compliant with United States regulatory standards. Notably, the new ISO 81060-2:2013 supersedes the previous 2009 version of this standard, and this study is being conducted in accordance with the most recent applicable ISO standard. ISO 81060-2:2013 standard provides a well-accepted set of requirements for the clinical assessment of sphygmomanometers used for intermittent, non-invasive, automatic estimation of arterial blood pressure using blood pressure cuffs against gold standard IBP measurement. This standard provides an objective basis for the assessment of all sphygmomanometers that sense or display pulsations, flow, or sounds in order to generate estimations, displays, or recordings of blood pressure in human patients. Notably, these standards are applied broadly across devices that use very different blood pressure assessment algorithms. The basis of this standard is comparison of the studied NIBP assessment devices to widely-accepted gold standard invasive blood pressure (IBP) measurement, less commonly referred to as intra-arterial blood pressure (IABP).

#### Noninvasive Blood Pressure (NIBP) vs. Gold Standard Intra-Arterial Invasive Blood Pressure (IBP) measurements

Direct blood pressure readings taken from major arteries, such as the aorta, are considered the gold standard in blood pressure assessment. In adults, IBP is a very common procedure used in Intensive Care Units that involves advancing a catheter into a major artery for continuous blood pressure monitoring. Umbilical artery catheters are also among the most commonly used blood pressure monitoring methodologies in neonatal intensive care units, in part because of their high accuracy. Because of the notable risks associated with arterial catheterization,

alternative NIBP measurements have also become routinely used in modern clinical practice. Numerous studies, have, however reported discrepancies between the blood pressure measurement provided by NIBP devices measurements and IBP measurements, particularly in special patient populations such as those with cardiac disease. Thus, contemporary NIBP algorithms should be validated against highly accurate gold standard IBP measurements to ensure accuracy and reliability of these devices.

### **Oscillometric NIBP Measurement**

The basic physiological principles that underlie NIBP technologies were first documented in the mid-1970s, and significant improvements have since been made in the algorithms that drive NIBP assessment. In the past decade, there has been increasing theoretical discourse regarding the optimal methods for evaluation of arterial mechanical properties and blood pressure pulse using noninvasive oscillometric maximum amplitude algorithm (MAA) estimates of the mean blood pressure obtained with air-filled occlusive cuffs. These data, once collected, can be mathematically extrapolated from experimental IBP measurements and waveform simulations and then recorded as exponential models. Most recently, automatic NIBP measurement systems have come to market that use highly specialized software algorithms to account for cuff pressure oscillations caused by the peripheral flow of blood either as discrete intervals or areas under a curve, allowing greater accuracy to be achieved using NIBP monitoring methods. As a result, modern NIBP algorithms are generally more accurate than their predecessors.

Noninvasive indirect oscillometric determination of blood pressure has significant advantages over invasive blood pressure assessments, as cuff inflation and deflation results in minimal discomfort and complications. Oscillometric NIBP assessment algorithms are able to noninvasively estimate systolic, mean, and diastolic pressure. In fact, this technique has become so popular that one survey reported more than 400 commercial device employing monitors that use NIBP algorithms available from numerous suppliers worldwide, though the accuracy of these models vary widely and may be poor in certain patient subpopulations.

Both the Datex-Ohmeda GE algorithm and the DINAMAP® SuperSTAT algorithms investigated in this study are oscillometric algorithms for assessment of NIBP from data collected using an occlusive air-filled cuff.

## **2.2. Pre-Clinical (animal) Trials and Previous Clinical (human) Experience**

Previous study has indicated that the GE DINAMAP® SuperSTAT algorithm on the GE CARESCAPE Patient Monitor Series or DASH® Monitor Series is accurate in adult, children, and neonate patients, including hypotensive and hypertensive patients. Furthermore, the GE DINAMAP® SuperSTAT algorithm and the Datex Ohmeda GE algorithm have also been reported to satisfy the ANSI/AAMI SP10-2002 and SP10A-1996 American National Standard for Electronic or Automated Sphygmomanometers in adults and, for GE DINAMAP® SuperSTAT only, neonatal populations, meaning that all values were  $\pm 5$  mmHg with a standard deviation of  $\leq 8$  mmHg of reference standards.

The Datex-Ohmeda GE algorithm has been successfully used to monitor blood pressure in adult patients and to predict vascular change and fluid loading, demonstrating results similar to

reference standard intra-arterial monitors in 26 patients according to the Association for Advancement of Medical Instrumentation (AAMI) standards. Compared to other oscillometric blood pressure measurement algorithms, Datex Ohmeda GE was shown to be somewhat slower but equally accurate in a study involving 160 blood pressure recordings.

## 2.3. Device Risk Analysis

Participation in this study has no direct benefit to participants; however, participants may benefit from more reliable assessment of blood pressure readings during their procedure due to the use of multiple devices and multiple recordings for blood pressure measurement. The NIBP device does not pose additional risks to patients, but there are risks associated with the additional IBP comparator procedures above the required clinical care for participating subjects. Use of existing indwelling lines in very young patients is designed to minimize additional disruption of care in pediatric patients.

The NIBP measurement (PDM-SuperSTAT and PSM-Datex-Ohmeda) devices and all patient monitors used in this study under study are commercially available, and all devices will be used according to their labeling. The GxP-validated GEHC PDM Data Collection Module may, when possible, be used to enable digital export of research data typically displayed on patient monitors.. The GxP-validated GEHC PDM Data Collection module works in the same way as the commercially available PDM module, but also has software to enable digital export of the data for research use. The validated non-commercial DC-EDIT and DC-COLLECTOR equipment for the DASH® 4000 and GEHC PDM Data Collection Module serve as a data output connections only and are not expected to impact the clinical function of the device. Participation in this study is not expected to impact patient management, clinical diagnosis, or treatment strategy compared to that which would be determined by the standard of care outside of this study.

### 2.3.1. Risk Analysis for Subjects with Indwelling Lines (≤29 days of age)

Eligible subjects aged 29 days or less will be recruited only if they currently have, or are scheduled to have, an indwelling femoral, radial, or umbilical arterial monitoring line placed. The type of line places will be determined according to the site standard of care, and not altered based on participation in the study. While radial lines are the most commonly placed indwelling lines in neonates, femoral and umbilical lines share a similar safety profile and, in some cases, are preferred in order to preserve integrity of vessels when future interventions may be required. Like radial and femoral line placements, umbilical lines have been shown to have a minimal complication rate even during longer procedures when performed by experienced physicians. For these subjects, NIBP measurements will be taken in a minimally disruptive manner in order to minimize possible interruption in their care. No additional lines will be placed for study purposes. These patients may participate for up to three days, taking as few determinations as necessary to accomplish research objectives each day under the supervision of a medically qualified investigator. There is not expected to be a significant risk to subjects based on placement of measurement devices in this study.

### **2.3.2. Risk Analysis for Subjects undergoing Non-Emergent Aortic Catheterization (aged >29 days to adult)**

Patients aged 29 days or older having prescribed non-emergent aortic catheterization procedures will be enrolled. Typical catheterization procedures in pediatric patients involve the use of general anesthesia for the duration of the clinically indicated procedure. The risks associated with general anesthesia are well documented and are widely considered safe when prudently administered. Due to study participation, the duration of general anesthesia may be slightly increased by a period of about 25 minutes (1-2 minutes for each study NIBP measurement), after which no further research procedures will be performed. General anesthesia is widely recognized as a neuromodulator with potential neurotoxic effects; however, it is widely believed that prudent use of general anesthesia in pediatric patients does not pose significant acute or chronic risks to patients at routine clinical dosages and non-repeating administrations. As used in this study, the devices and study procedures are not expected to pose significant risks to participating subjects beyond those of their clinically indicated catheterization procedure.

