## 6.5. Exclusion Criteria

Subjects will be excluded that:

1. Have previously participated in this study (no subject may participate more than once).
2. Exhibit signs or symptoms or have a current diagnosis of peripheral vascular disease in upper AND/OR lower limbs;
3. Have current, uncontrolled circulatory shock;
4. Exhibit injuries, deformities, intravenous lines, or other abnormalities that, in the opinion of the investigator, may prevent proper cuff application or functioning;
5. For women of child-bearing potential, are currently pregnant, suspected to be pregnant, or are currently lactating;
6. Have any condition that could interfere with the subjects ability to tolerate the procedure, including having a maximum of 4 fast flushes (adult, adolescent, or pediatric patients aged >29 days) or 1 fast flush (neonates aged <29 days);
7. If aged greater than 29 days but less than 12 years of age, have previously had any clinical or research procedure requiring general anesthesia in the last 3 month period;
8. If aged greater than 29 days but less than 12 years of age, are expected to require more than three (3) total hours of continuous general anesthesia for the scheduled procedure (including clinically necessary anesthesia and anticipated 25 minute extension for study purposes).

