### 7.2.4. Blood Pressure Assessments

NIBP will be measured using the CARESCAPE Monitor B650 patient monitor equipped with an acquisition module (either PDM-SuperSTAT or PSM-Datex-Ohmeda, determined by study arm). IBP will be measured using the DASH® 4000 plus DC-COLLECTOR and DC-EDIT software. For PDM procedures where the PDM Data Collection Module is used for electronic data capture, this may be used in place of manual transcription from the patient monitor to paper CRFs. During the blood pressure assessments, values will be recorded for:

1. Study Arm
2. Time of first and last blood pressure measurement
3. Systolic, Diastolic, Mean, Test Duration
4. If the prescribed wait time was taken between tests
5. Any measurements with no determination

Both NIBP and IBP assessments will be conducted simultaneously, using either digital data recording tools (when available) or recorded by hand onto a paper Case Report Form (CRF). If

necessary, assistance will be provided by other study staff to ensure that accurate and simultaneous blood pressure data is recorded.

IBP data will be continuously collected throughout the study.

For cases where manual data collection of NIBP data is necessary, it will be recorded according to the following procedure:

1. Use the patient monitor equipped with either PDM-SuperSTAT or PSM-Datex-Ohmeda according to the patient's study arm to determine the patient's blood pressure.
2. Clear the patient monitor memory of the previous determination and wait at least 3 min
3. Have the observers using the reference IBP monitoring equipment (DASH® 4000) and the NIBP monitoring equipment (CARESCAPE Monitor B650 with either PSM or PDM) simultaneously record and determine the patient's blood pressure, as follows.
  - a. Start continuous collection on the IBP DCS system at the same time as recording of NIBP begins
  - b. Collect each NIBP measurement from the CARESCAPE Monitor B650
4. Wait the appropriate amount of time between determinations (as defined in [Table 2](#)).

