5. Repeat steps 3 and 4 adhering to the requirements in [Table 2](#) until the target number of recordings and determinations have been performed or the subject leaves the study. In the event that any blood pressure determination is not successful, the procedure may be repeated to achieve the target number of successful blood pressure determinations. No more than the maximal number of total blood pressure determinations as specified in [Table 2](#) will be performed on any patient.
6. When all NIBP measurements are complete, stop the IBP data collection.

For PDM procedures where the PDM Data Collection Module is used, data may be captured electronically instead of using the manual procedure according to the following procedure:

1. Use the PDM Data Collection Module to determine the patient's blood pressure.
2. Wait at least 3 min.
3. Simultaneously record and determine the patient's blood pressure, as follows.
  - a. Start NIBP measurement from the PDM Data Collection Module
4. Wait the appropriate amount of time between determinations (as defined in [Table 2](#)).
5. Repeat steps 3 and 4 adhering to the requirements in [Table 2](#) until the target number of recordings and determinations have been performed or the subject leaves the study. In the event that any blood pressure determination is not successful, the procedure may be repeated to achieve the target number of successful blood pressure determinations. No more than the maximal number of total blood pressure determinations as specified in [Table 2](#) will be performed on any patient.
6. When all NIBP measurements are complete, stop the data collection.

The same number and type of determination should be performed whether the manual or digital PDM Data Collection Module is used.

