**Table 2 – Number of Blood Pressure Assessments and Frequency**

Population	Maximum Number of BP Determinations	Target Number of Valid BP Determinations	Frequency of Determinations
Pediatric, Adolescents, and Adults (aged ≥ 3 years)	15 max attempts	10 determinations	At least 60 s between determinations
Children & Infants (<3 years old to >29 days old)	10 max attempts	10 determinations	At least 60 s between determinations
Neonates (< 29 days old)	10 max attempts	5-10 determinations	At least 3 minutes between determinations (over max of 72 hours)

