## 9.5. Handling of Missing Data

Every effort will be made to obtain complete data. Data analysis will be based on collected data. Missing data will not be imputed using any imputation methods. Missing data is not expected for blood pressure values because up to 15 blood pressure determination procedures will be allowed, if necessary, to obtain 10 blood pressure recordings, thus minimizing the likelihood of missing data in IBP and NIBP blood pressure determination pairs. Any pair of blood pressure measurements with a missing value will be excluded from analysis.

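### Section 2.3.2 describes research ending after about 25 minutes of added anesthesia, but the procedures in 7.2.4 limit only the count, so a series with repeats at ages 3 to under 12 may run longer

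*Combined protocol and SAP*

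**What the plan says.** Section 2.3.2 covers subjects over 29 days old who undergo catheterization. It says that anesthesia may be "increased by a period of about 25 minutes (1-2 minutes for each study NIBP measurement), after which no further research procedures will be performed". Sections 2.3.3 and 11.1 repeat the figure as an approximation. Exclusion criterion 8 in 6.5 applies from over 29 days to under 12 years. It limits expected anesthesia to three hours, "including clinically necessary anesthesia and anticipated 25 minute extension for study purposes".

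Section 7.2.4 gives the bedside procedure:

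- Step 1 takes an initial reading.
- Step 2 of the manual procedure is "Clear the patient monitor memory of the previous determination and wait at least 3 min"; the electronic procedure has the same wait.
- Step 3 takes a study reading, and step 4 is the Table 2 wait.
- Step 5 repeats these "until the target number of recordings and determinations have been performed or the subject leaves the study". After a failed reading, "the procedure may be repeated to achieve the target number of successful blood pressure determinations", up to the Table 2 maximum.

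The two procedures match on this point: "The same number and type of determination should be performed whether the manual or digital PDM Data Collection Module is used".

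Table 2 puts children from age 3 in the same row as adults: "15 max attempts", a target of 10, and at least 60 seconds between readings. Section 9.5 confirms that "up to 15 blood pressure determination procedures will be allowed, if necessary, to obtain 10 blood pressure recordings". Children over 29 days and under 3 years have a target of 10 and a cap of 10. Neither of these rows sets a maximum spacing or a total time.

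**The concern.** The 25 minutes appears in the risk sections and in an eligibility test. The instructions that a site follows during the procedure do not mention it: a series there is limited by a count, never by a clock. Section 7.4 lets the investigator withdraw a patient at any time, but nothing links that to minutes of study time.

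Other text favors continuing. Section 9.5 asks for every effort to get complete data, and 6.3.1 says incomplete datasets do not count toward the Table 1 minimums. Section 6.2 points to Table 2 for added limits on sampling in pediatric subjects, yet from age 3 the limits there are the adult ones.

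The children concerned may be under general anesthesia, and the protocol itself treats longer anesthesia at these ages as a risk to be contained. A site could follow step 5 exactly and go past the extension described in the risk sections.

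**Working it through.** **Inputs.** Minutes per reading, d = 1 to 2 (2.3.2; 1.5 is used as the midpoint). First wait 3 minutes (7.2.4, step 2). Gap between readings 1 minute (Table 2). Attempt cap 15 from age 3, and 10 from over 29 days to under 3 years (Table 2). The waits are minimums and calibration flushes are not counted, so these times are not upper limits for the series.

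**Formula.** With m readings after the initial one, T = d + 3 + m·d + (m − 1)·w. Here w = 0 if the 1–2 minutes already includes the 60-second wait, and w = 1 if the wait is a separate step, as steps 3 and 4 read. The text does not say whether the initial reading counts toward the cap, so both cases are given.

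**The plan's own figure.** Ten readings after the initial one, d = 2, wait included: 2 + 3 + 20 = 25 minutes. A second route comes close: 15 attempts at 1.5 minutes give 15 × 1.5 + 3 = 25.5, or 16 × 1.5 + 3 = 27 with the initial reading extra. The documents do not show which was meant.

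**Fifteen attempts (ages 3 to under 12), minutes:**

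| | d = 1 | d = 1.5 | d = 2 |
|---|---|---|---|
| Wait included, initial counted: 15d + 3 | 18 | 25.5 | 33 |
| Wait included, initial extra: 16d + 3 | 19 | 27 | 35 |
| Wait separate, initial counted: 15d + 3 + 13 | 31 | 38.5 | 46 |
| Wait separate, initial extra: 16d + 3 + 14 | 33 | 41 | 49 |

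At 2 minutes each, the 15 readings alone take 30 minutes before any wait.

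**Ten attempts (the cap under age 3; also ages 3 and over without repeats), minutes:**

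| | d = 1.5 | d = 2 |
|---|---|---|
| Wait included: 10d + 3, or 11d + 3 | 18 or 19.5 | 23 or 25 |
| Wait separate: 10d + 3 + 8, or 11d + 3 + 9 | 26 or 28.5 | 31 or 34 |

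Under age 3, then, repeats cannot lengthen a series past 10 attempts, but with a separate wait even 10 attempts exceed 25 minutes at these durations.

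**Effect of a 25-minute stop**, if the whole series falls in the timed period. With a separate wait, attempt n after the initial reading starts at d + 3 + (n − 1)(d + 1). The last one to start before minute 25 is n = 11, 9 and 7 for d = 1, 1.5 and 2. With the wait included, the start is d + 3 + (n − 1)d, which leaves 10 attempts at d = 2 and more at shorter d. A reading begun just before minute 25 ends by minute 27.

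**Pairs from age 3 at the Table 1 minimums**, with 10 valid readings per adult or adolescent and r per child: PDM (15 + 7) × 10 + 5r; PSM 15 × 10 + 5r.

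| r | PDM | PSM |
|---|---|---|
| 10 | 270 | 200 |
| 7 | 255 | 185 |
| 4 | 240 | 170 |
| 0 | 220 | 150 |

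The target in 6.3 is at least 150 per arm. With children at 7, PSM reaches it if its 15 adults and adolescents average (150 − 35)/15 = 7.7 valid readings; with children at 10, (150 − 50)/15 = 6.7.

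**The case against.** The strongest reply is that nothing is broken. Section 2.3.2 is current protocol text and staff are trained on the whole protocol (8.2), so if it is a stop, it already binds. It may not be a stop at all: the clause can mean that once the readings are done, no other research follows. Every mention of 25 minutes is hedged as an estimate, and 15 attempts at 1.5 minutes with the wait included nearly match it. The times above are series times, and readings taken alongside clinical work add no anesthesia. Controls also exist: an attempt cap, repeats that are optional, investigator withdrawal, and the three-hour enrollment limit.

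Much of this stands. A reader might infer that 2.3.2 and 7.2.4 contradict each other, that exclusion 8 is breached, or that 15 attempts must be made and 25 minutes will be exceeded. The documents support none of these. The figure is approximate, exclusion 8 tests what is expected at enrollment, repeats are permitted rather than required, and some readings of the timing fit.

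The reply does not close the gap. If 2.3.2 is a stop, step 5 tells sites to carry on past it. If it is only an estimate, the added anesthesia has no time limit during the procedure.

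**Conclusion.** The statement in 2.3.2 is not carried into the procedure that sites follow. At ages 3 to under 12, a series that uses all 15 attempts at 2 minutes each takes 33–35 minutes with the wait included and 46–49 with it separate. At 1.5 minutes with the wait included it takes 25.5–27 and fits. An overrun is therefore possible, and whether it occurs depends on cuff time, on how the 60 seconds is counted, and on how many repeats are needed. These times equal added anesthesia only if the readings do not overlap clinical work, which the documents do not state.

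For children over 29 days and under 3 years the issue is narrower. Their cap is already 10 attempts, and the open question is whether the 1–2 minutes includes the wait.

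The change is worth making because it limits anesthesia in children at a small cost in readings.

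**What to change.** - **7.2.4, step 5 of both procedures.** For children aged 3 to under 12 under general anesthesia, start no new study reading once anesthesia has been continued for 25 minutes solely for study readings, even if 10 valid readings have not been reached. The clock starts when the clinically indicated work is complete or is paused for the study.
- **9.5.** Note that such series may end short, and that their valid pairs stay in the analysis.
- **6.3.1.** Do not treat a series as incomplete only because this stop ended it, so that it does not lead to enrolling another child. This and the retention of pairs apply unless ISO 81060-2:2013, which is not reproduced in the protocol, requires otherwise.
- **2.3.2, for children over 29 days and under 3 years.** State whether the 1–2 minutes includes the 60-second wait. If it does not, restate the 25 minutes and use the same figure in 2.3.3, 11.1 and exclusion 8.

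The cost is a few sentences, one clock time for sites to note, and some pediatric series with fewer than 10 readings. The pair target has room for this at the Table 1 minimums. The margin is thinner in the PSM arm and depends on its adults and adolescents giving close to their 10 valid readings.
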